## 7.5 Lost to Follow-up

A subject will be considered lost to follow-up if he or she repeatedly fails to return for scheduled visits and is unable to be contacted by the study site.

The following actions must be taken if a subject fails to return to the clinic for a required study visit:

• The site must attempt to contact the subject and reschedule the missed visit as soon as possible and counsel the subject on the importance of maintaining the assigned visit

schedule and ascertain whether or not the subject wishes to and/or should continue in the study.

- Before a subject is deemed lost to follow up, the investigator or designee must make
  every effort to regain contact with the subject (where possible, 3 telephone calls/emails,
  and if necessary, a certified letter to the subject's last known mailing address or local
  equivalent methods). These contact attempts should be documented in the subject's study
  records.
- Should the subject continue to be unreachable, he/she will be considered to have withdrawn from the study with a primary reason of lost to follow-up.

#### 7.6 Termination of the Clinical Study

The Sponsor designee reserves the right to close the study site(s) or terminate the study at any time for any reason at the sole discretion of the Sponsor. Study sites will be closed upon study completion. A study site is considered closed when all required documents and study supplies have been collected and a study-site closure visit has been performed.

The investigator may initiate study-site closure at any time, provided there is reasonable cause and sufficient notice is given in advance of the intended termination.

Reasons for the early closure of a study site by the sponsor or investigator may include but are not limited to:

- Failure of the investigator to comply with the protocol, the requirements of the IRB/IEC or local health authorities, the Sponsor's procedures, or Good Clinical Practice (GCP) guidelines
- Inadequate recruitment of participants by the investigator
- Discontinuation of further study treatment development

#### 8 STATISTICAL METHODS

Before database lock, a statistical analysis plan (SAP) will be issued as a separate document, providing detailed methods for the analyses outlined below. Any deviations from the planned analyses will be described and justified in the clinical study report.

## 8.1 Populations for Analysis

#### 8.1.1 MITT population

The modified intent-to-treat (mITT) population will include all randomized subjects who took at least one dose of the study medication and who completed both an ADAS-Cog13 and ERP P300 assessment at Baseline and during at least one post-baseline visit. Subjects will be analyzed according to the dose they were randomized to.

#### 8.1.2 Per protocol population

The per protocol population will include all mITT subjects who were medication compliant during the 26 weeks of double-blind treatment (as defined in Section 5.6) and completed both an ADAS-Cog13 and ERP P300 assessment during at least one post-baseline visit, and did not have any major protocol deviations. Subjects will be analyzed based on actual treatment received.

## 8.1.3 Safety population

The Safety population will include all randomized subjects who received at least one dose of the study medication. Subjects will be analyzed based on actual treatment received.

#### 8.2 General Considerations

Descriptive statistics for continuous variables will include number of subjects (n), arithmetic mean, standard deviation, median, minimum, maximum and first and third quartile limits unless otherwise noted. Frequency and percentage will be calculated for categorical variables.

Change from baseline is calculated by subtracting the baseline score from the observed value at any subsequent visit. For safety summaries, the last pre-randomization measurement is defined as the baseline value. For clinical effect measures baseline is defined as the last pre-randomization measurement.

Percentages are based on the number of subjects in each treatment group in the given population for AE summary tables, and additionally overall for medical history, prior and concomitant medications. For all other tables, percentages are based on the number of subjects with non-missing data in each treatment group and overall for the given population.

### 8.3 Clinical Effect Analyses

## 8.3.1 Primary Clinical Effect Analysis - GST

The primary hypothesis is that treatment with ATH-1017 will result in a statistically significant reduction in change from baseline in the GST score (O'Brien, 1984) (combining the ADAS-Cog13 score and the change from baseline in ERP P300 at Week 26) relative to the placebo group in the mITT population. The primary analysis will test the statistical hypothesis of no difference between placebo and 70 mg ATH-1017 first and then 40 mg ATH-1017 versus placebo.

The primary analysis will use a mixed model with repeated measures (MMRM) to compare the estimated change from baseline between active treatment and placebo in the GST score. This analysis will assess whether or not there is a difference in estimated GST values between treatment groups and placebo at 26 weeks using least squares means estimates from the MMRM model, and will include terms for baseline, baseline by time interaction, and baseline by time by treatment interaction in the model. Additional terms will be included for GBA genotype, and site (with smaller sites grouped), and age. Least squares means and standard errors will be estimated from the MMRM model at Week 26. Further details relating to the primary analysis will be described in the SAP.

## 8.3.2 Secondary Analysis – ADAS-Cog13 and ERP P300

The separate secondary variables of ADAS-Cog13 and ERP P300 will be analyzed using the same MMRM model that was used for analysis of the primary endpoint.

## 8.4 Safety Summaries

The Safety population will be used for analyses of each of the safety endpoints. All concomitant medications will be tabulated according to drug class and preferred term using the World Health Organization Drug dictionary. Clinical laboratory tests, vital signs, physical and neurological examinations, and ECG results will be summarized by number of subjects, frequency rates and by treatment group. The timepoint of each event will also be summarized.

#### 8.4.1 Adverse Events

AEs occurring after the start of study drug dosing on Day 1 will be summarized descriptively for the Safety population. All AEs will be coded according to system organ class and preferred term using a Medical Dictionary for Regulatory Activities dictionary. Summary tables showing the number of subjects and percentage within each category will be generated for each of the following types of AEs:

- All events
- Serious events
- Deaths
- Events leading to study discontinuation
- Events related to study treatment (study drug and injection procedure separately)
- Severe events

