#### 6 STUDY DESIGN CONSIDERATIONS

This study (ATH-1017-PD-0201) is designed to demonstrate as a safety and proof of concept study of ATH-1017 in PDD and DLB subjects. Eligible participants will receive once daily (OD) subcutaneous (SC) injections of ATH-1017 (40 mg or 70 mg) or placebo, over a 26-week double-blind period, followed by a 4-week safety follow-up.

NOTE: This study was stopped early; safety listings and summaries will be performed as previously envisioned; however efficacy and biomarker analyses will be exploratory in nature.

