#### **10.6.1** Adverse Events

All adverse events will be coded using the most current version of the Medical Dictionary for Regulatory Activities (MedDRA). A treatment-emergent adverse event (TEAE) is defined as any adverse event that begins or worsens in severity on or after the first study drug dose date until follow-up period. Treatment Related AE includes probably related, possibly related or related AEs. Injection Site Reactions will be identified from high level term (HLT) as 'Injection Site Reactions'.

The number and percentage of subjects experiencing one or more adverse events in the following adverse event categories will be summarized for each treatment group, and overall. No comparisons of treatment groups will be performed.

- Any AE
- Any TEAE
- Any Treatment Related TEAE (possibly related; probably related; related)
- Any severe TEAE

Confidential Page 38 of 57

- Any serious TEAE
- Any TEAE that led to discontinuation of study drug
- Any fatal TEAE
- All deaths

Treatment emergent adverse event (TEAE) incidence will be summarized and presented using primary MedDRA system organ classes (SOCs), and preferred terms (PTs).

- All TEAE
- Any Treatment Related-TEAE
- Study Drug Related Treatment-Emergent Adverse Events by Worst Severity
- Any serious TEAE by Worst Severity
- Any TEAE that led to discontinuation of study drug
- Treatment-Emergent Adverse Events Leading to Death
- Injection Site Reactions Treatment-Emergent Adverse Events

The following listings of adverse events will be prepared.

- All adverse events
- Drug Related Treatment-Emergent Adverse Events
- Injection Site Reactions Treatment-Emergent Adverse Events
- Serious Treatment-Emergent Adverse Events
- Treatment-Emergent Adverse Events Leading to Study Discontinuation
- Death listing

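### Severe TEAEs that are non-serious and judged unrelated cannot be identified as severe in any by-term table of the SAP; an all-cause severity table should be added

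*Protocol*

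**What the plan says.** Protocol 8.4.1 begins with coding: "All AEs will be coded according to system organ class and preferred term using a Medical Dictionary for Regulatory Activities dictionary". It then says: "Summary tables showing the number of subjects and percentage within each category will be generated for each of the following types of AEs". Six types follow: all, serious, fatal, leading to study discontinuation, treatment-related, and "Severe events". The last has no causality or seriousness condition.

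SAP 10.6.1 plans three layers of output.

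- **Overview table.** Subjects with "adverse events in the following adverse event categories will be summarized for each treatment group, and overall". One row counts subjects with any severe TEAE, whatever its cause.
- **SOC/PT tables.** Seven are listed. Two carry severity: "Study Drug Related Treatment-Emergent Adverse Events by Worst Severity" and "Any serious TEAE by Worst Severity". The other five (all TEAEs, treatment-related TEAEs, TEAEs leading to stopping study drug, TEAEs leading to death, injection site reactions) have no severity split.
- **Listings.** These include one of all adverse events. The SAP does not say which columns it shows.

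On the early stop, SAP Section 6 says that "safety listings and summaries will be performed as previously envisioned". SAP Section 8 sets out the changes from the protocol, and none of its items concerns adverse event tables.

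**The concern.** Whether a by-term table shows that an event was severe depends, for non-serious events, on the investigator's causality call. If the event is judged related, it appears with its severity under its preferred term. If it is judged unlikely related or unrelated, it adds one to an overview count and appears under its term without a severity label.

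This matters more here than in many trials. Safety and tolerability are a primary objective, and SAP Section 6 makes the efficacy and biomarker analyses exploratory, so the safety tables are the main output. Protocol 6.4.1.1 keeps expected signs of the underlying disease out of the adverse event data unless they are worse than expected for that subject. Protocol Table 3 says that unrelated events are typically explained by factors such as concomitant disease. A severe worsening that resembles Parkinson's disease dementia or dementia with Lewy bodies could therefore be recorded as an adverse event and then classed as unrelated. A reader of the summary tables would see how many subjects had a severe event. The reader could not see whether the non-serious, unrelated ones in an arm were one recurring term or several different ones.

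**Working it through.** No arithmetic applies: the point concerns table content, and neither document states an adverse event rate. The check has three steps.

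**Step 1. Which severe TEAEs can be recognised as severe by term?** A severe event need not be serious; both documents say so under Seriousness and give headache as an example. Protocol 6.4.1.3 (Causality) counts related, probably related and possibly related as related. That leaves unlikely related and unrelated, together called unrelated here. Crossing causality with seriousness gives four kinds:

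| Severe TEAE | Overview row for severe TEAEs | All-TEAE SOC/PT table (no severity) | Drug-related by severity, SOC/PT | Serious by severity, SOC/PT | Recognisable as severe by term? |
|---|---|---|---|---|---|
| Related, serious | yes | yes | yes | yes | yes |
| Related, non-serious | yes | yes | yes | no | yes |
| Unrelated, serious | yes | yes | no | yes | yes |
| Unrelated, non-serious | yes | yes | no | no | **no** |

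Three of the four kinds are covered and one is not. The missed kind is still counted in the overview and still appears by term; what it lacks is the severity label.

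**Step 2. Does each protocol type have an SOC/PT table in the SAP?**

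| Protocol 8.4.1 type | SOC/PT table in SAP 10.6.1 |
|---|---|
| All events | yes |
| Serious events | yes, by worst severity |
| Deaths | yes |
| Leading to study discontinuation | yes, worded as stopping study drug |
| Related to study treatment | yes |
| Severe events | none; overview row only |

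Five of six types have one. Severe events are the exception.

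**Step 3. What does the protocol mean by category?** The sentence in Protocol 8.4.1 asks for subjects and percentages within each category, for each type. It therefore treats category and type as different things. The only classification named in that paragraph before the list is SOC and PT, so a by-term table per type is the most natural reading. The SAP's treatment of the other five types fits it. The protocol does not say so outright.

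**The case against.** The strongest reply is that the protocol is already satisfied. Its SOC/PT sentence is about coding, not table layout. If category simply means the type of event, the overview row gives what is asked: number and percentage of subjects with a severe TEAE, by arm, whatever the cause. Nothing would then have changed, and SAP Section 8 would have nothing to declare. This reading is possible, so a breach of the protocol is not established. It does leave unexplained why severe events alone among the six types have no by-term table.

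Three further replies have weight.

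- Severity is recorded for every adverse event (Protocol 6.4.1.2), and a listing of all adverse events is planned. In a small trial, individual severe events can be read there if severity is shown. The SAP does not say that it is, and a listing is not a summary by arm.
- Severe and serious overlap. Severe means a substantial influence on daily activities, and serious includes substantial disruption of normal life functions, so the missed group may be small.
- SAP 10.6.1 plans no comparison of treatment groups for adverse events, so no formal test is affected.

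A reader might also infer three stronger conclusions, which the documents do not support.

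- *That severe unrelated events are absent from every by-term table.* They are not: all of them are in the all-TEAE table, and the serious ones are also in the serious-by-severity table, which has no causality filter.
- *That the drug-related severity table is shown to be biased between arms.* Attribution could differ by arm, but the documents give no attribution or reaction rates, and placebo is injected too. Any figure would rest on invented rates.
- *That the discontinuation tables count something materially different.* The SAP tabulates "Any TEAE that led to discontinuation of study drug", while Protocol 8.4.1 and the SAP's own listing refer to study discontinuation. Protocol 7.4.1 withdraws from the study every subject who permanently stops treatment, so the two counts should nearly coincide. This is wording to align.

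**Conclusion.** The point holds in a narrow form. SAP 10.6.1 has no SOC/PT table that shows severity for all TEAEs, and no SOC/PT table of severe TEAEs. One of the four kinds of severe TEAE, non-serious and judged unrelated, therefore cannot be identified as severe in any by-term table.

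The coverage gap rests only on the table list in SAP 10.6.1. That it also departs from the protocol rests on the more natural, but unstated, reading of category in Protocol 8.4.1. How many events fall in the gap is unknown, and with early closure it may be few. This is an inexpensive improvement that should be made to the reporting of a primary safety objective; it does not threaten the safety conclusions as a whole.

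**What to change.** In SAP 10.6.1, add a table of all TEAEs by SOC, PT and worst severity, by arm, and keep the drug-related version as a subset. A by-term table restricted to severe TEAEs would also close the gap. Either one meets Protocol 8.4.1 under both readings and removes the dependence of by-term severity on the causality judgment. If the sponsor prefers to add neither, SAP Section 8 should state that severe events are reported only as an overview count.

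At the same edit, use one wording for discontinuation in the tables and the listing, matching Protocol 8.4.1.

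The cost is SAP wording and one more table from data already collected. SAP 9.1 presents safety data by disease type and by acetylcholinesterase inhibitor use within it, so the table may be repeated across those strata, with sparse cells. The only downside is the extra output.

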#### 8.4.2 Laboratory parameters

Laboratory parameters and vital signs will be summarized by visit. Frequencies of high and low values with respect to the normal range will be displayed, as will shift tables comparing results at each treatment visit.

## 8.4.3 12-Lead Electrocardiogram

12-lead ECG data (observed and change from baseline) will be listed for each subject by visit. Observed values and change from baseline will be summarized descriptively.

### 8.4.4 Columbia-Suicide Severity Rating Scale

Results from the C-SSRS questionnaire will be listed and summarized using descriptive statistics by treatment group and visit.

## 8.4.5 Geriatric Depression Scale

Results from the GDS questionnaire will be listed and summarized using descriptive statistics by treatment group and visit.

## 8.6 Determination of Sample Size

A total sample size of 75 evaluable subjects (25 per treatment arm) was chosen empirically for this proof-of-concept study based on ERP P300 latency results obtained in the Phase 1a/b study, NDX-1017-0101; no formal sample size calculation was applied.

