baseline visit (Visit 2b, Baseline, Day 1), no more than 10 days after the Pre-baseline visit, eligible subjects will be randomized in a ratio of 1:1:1 to receive ATH-1017 40 mg/day, ATH-1017 70 mg/day, or placebo. At this Baseline visit (Visit 2b), subjects will undergo pre-dose baseline and post-dose ERP P300. Study drug will be administered by subcutaneous (SC) injection once-daily (OD) preferably during daytime; subjects must not take another dose within 8 hours of the preceding dose. The first SC injection of study drug will be performed on site under supervision. The subject should withhold study drug administration on the day of subsequent clinic visits; study drug administration will be done on site under supervision of site staff at these visits. Each subject is required to have a primary caregiver willing to accept responsibility for supervising or, if required, administering study drug, and assessing the condition of the subject throughout the study in accordance with all protocol requirements. During the double-blind treatment period, clinic visits will take place on Day 1 and thereafter at Weeks 2, 6, 12, 16, 20, and 26, with a safety follow-up visit scheduled 4 weeks after completion of the double-blind period at Week 30 (see Table 1 for Schedule of Assessments). On Day 1, after completion of the first dose, subjects will remain on-site for 2 hours for post-treatment ADAS-Cog13, clinical observation. assessments shall occur at clinic visits in the morning at approximately the same time they were performed during the initial baseline assessment (Visit 2b). Subjects will undergo post-baseline ERP P300 at clinic visits (pre- and/or post-dose timepoints) as specified in Table 1. Subjects may live at home, in a senior residential setting, or an institutional setting without the need for continuous nursing care, and should not be likely to experience a change in living conditions (e.g., institutionalization, moving to a different city, etc.), or change in primary caregiver, during participation in the trial period. The end of the study is defined as the date of the safety follow-up visit, Visit 9/Week 30. Subjects who terminate prior to Visit 8 are to complete the same assessments as Visit 8/early termination (ET). Blood draws will take place at scheduled clinic visits for analysis of plasma concentrations of ATH-1017 (pro-drug) and ATH-1001 (active metabolite). **Treatments** Subjects will be randomized to one of 3 treatment groups: Administered: ATH-1017, 40 mg, OD, SC ATH-1017, 70 mg, OD, SC Placebo, OD, SC An interim analysis of pharmacodynamics (ERP P300 latency) and safety is planned for when at least 30 subjects have completed their Week 2 assessment. Subjects subsequently recruited may be randomized to only 1 of the 2 doses of ATH-1017 (either 40 mg or 70 mg, OD, SC) in a 2:1 ratio (ATH-1017:placebo); subjects already enrolled in the study will continue on their treatment as originally assigned. All personnel involved in the management and conduct of the study will remain blinded to dose assignments. Investigational Active Treatment: ATH-1017 will be presented in identical prefilled 1 mL syringes of **Medicinal Products:** 40 mg/mL and 70 mg/mL Placebo: Placebo prefilled 1 mL syringes matching active treatment **Number of Subjects:** The study will randomize approximately 75 subjects in a 1:1:1 ratio to either ATH-1017 40 mg, ATH-1017 70 mg, or placebo

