# 4.1 Number of Subjects

The study will randomize approximately 75 subjects in a 1:1:1 ratio to ATH-1017 40 mg, ATH-1017 70 mg, and placebo groups.

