Study drug will be administered by SC injection OD preferably during daytime; subjects must not take another dose within 8 hours of the preceding dose. The first SC injection of study drug will be performed on site under supervision. The subject should withhold study drug administration on the day of subsequent clinic visits; study drug administration will be done on site under supervision of site staff at these visits. Each subject is required to have a primary caregiver willing to accept responsibility for supervising or, if required, administering study drug, and assessing the condition of the subject throughout the study in accordance with all protocol requirements. During the double-blind treatment period, clinic visits will take place on Day 1 and thereafter at Weeks 2, 6, 12, 16, 20, and 26, with a safety follow-up visit scheduled 4 weeks after completion of the doubleblind period at Week 30 (see Appendix 2 for Schedule of Assessments). On Day 1, after completion of the first dose, subjects will remain on-site for 2 hours for post-treatment clinical ADAS-Cog13 assessments shall occur at clinic visits in the morning at approximately the same time they were performed during the initial baseline assessment (Visit 2b). Subjects will undergo post-baseline ERP P300 assessments at clinic visits (pre- and/or post-dose timepoints) as specified in Appendix 2.

Subjects may live at home, in a senior residential setting, or an institutional setting without the need for continuous nursing care and should not be likely to experience a change in living

Confidential Page 14 of 57

24

conditions (e.g. institutionalization, moving to a different city, etc.), or change in primary caregiver, during participation in the trial period. The end of the study is defined as the date of the safety follow-up visit, Visit 9/Week 30. Subjects who terminate prior to Visit 8 are to complete the same assessments as Visit 8/early termination (ET).

Double-Blind Placebo-Controlled Dosing (26-Weeks) Option to collapse 40 or 70 mg ATH-1017 arm for remainder of recruitment after Week 2 Interim Analysis (randomized 2:1) until 75 Screening Period (28 days) subjects enrolled Pre-Baseline (8 days) Randomization 1:1:1 I /0 mg ATH-101/ arm 40 mg ATH-1017 arm Safety Follow-up (4-Weeks)

Figure 1. Study Schema

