#### 6.1.2 Justification of Sample Size

Placebo arm

Interim analysis of ERP-P300 latency when 30 subjects complete Week 2

A total sample size of 75 evaluable subjects (25 per treatment arm) was chosen empirically for this proof-of-concept study based on ERP P300 latency results obtained in the Phase 1a/b study, NDX-1017-0101; no formal sample size calculation was applied.

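### The plan sets 75 evaluable subjects but randomizes only about 75, with no stated allowance for loss

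*Protocol*

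**What the plan says.** **Target size.** Protocol 8.6: "A total sample size of 75 evaluable subjects (25 per treatment arm) was chosen empirically". The synopsis (Sample Size Considerations) gives the same figure, and SAP 6.1.2 repeats it: "A total sample size of 75 evaluable subjects (25 per treatment arm) was chosen empirically for" this proof-of-concept study. All three add that no formal calculation was done.

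**Number randomized.** Protocol 4.1: "The study will randomize approximately 75 subjects in a 1:1:1 ratio". The synopsis (Number of Subjects) agrees.

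**Efficacy population.** Protocol 8.1.1 and SAP 7.1.2 limit mITT to randomized subjects who took at least one dose and completed both ADAS-Cog13 and ERP P300 at baseline and at a post-baseline visit. Neither document says that this is what evaluable means.

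**Interim option.** The synopsis (Treatments Administered) has an interim analysis "planned for when at least 30 subjects have completed their Week 2 assessment". After it, "Subjects subsequently recruited may be randomized to only 1 of the 2 doses of ATH-1017", at 2:1 active to placebo. The schema in SAP 6.1 keeps the total fixed: "Interim Analysis (randomized 2:1) until 75" subjects are enrolled. SAP 8, 9.4 and 10.5.5 cancel the interim because the trial stopped early.

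**The concern.** The number to be randomized equals the number said to be evaluable. Both hold only if essentially every randomized subject ends up evaluable, yet the plan itself foresees loss. Protocol 7.4.1 withdraws everyone who permanently stops treatment. Protocol 7.4.2 lists further discontinuation grounds such as nursing home placement and loss of the caregiver. Protocol 6.3 recognizes that motor disturbance can spoil P300 recordings, and Protocol 7.2 lets the Week 2 visit be held remotely in a pandemic.

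The sample-size sections also do not say that 25 per arm depends on both doses being kept. And SAP 6.1.2 was left unchanged when the rest of the SAP was revised for the early stop, so it still gives 75 evaluable without marking it as planned rather than achieved.

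What is at stake is how many subjects stand behind the t-tests and 95% confidence intervals that SAP 10.5 still specifies.

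**Working it through.** **The plan's own figure.** 3 arms × 25 = 75, so the total is internally consistent. It cannot be derived further, because the documents give no effect size, SD, power or loss rate.

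**Inputs.** Evaluable target 75, or 25 per arm (Protocol 8.6, SAP 6.1.2). Randomized about 75 at 1:1:1 (Protocol 4.1). Primary efficacy comparison in the SAP: pooled doses against placebo, with 95% intervals (SAP 10.5). Dose-specific comparisons in the protocol: 70 mg, then 40 mg, each against placebo (Protocol 8.3.1). Loss d is an assumption, shown from 5% to 20%, equal across arms.

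**Evaluable number from 75 randomized, and number to randomize for 75 evaluable.** Evaluable = 75(1 − d); required = 75/(1 − d), rounded up.

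| Assumed loss | Evaluable | Per arm | Randomize for 75 evaluable |
|---|---|---|---|
| 0% | 75 | 25 | 75 |
| 5% | 71.25 | 23.75 | 79 |
| 10% | 67.5 | 22.5 | 84 |
| 15% | 63.75 | 21.25 | 89 |
| 20% | 60 | 20 | 94 |

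The last column only sizes the gap; it is not a recommendation to enrol more.

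**95% CI half-width in SD units.** Half-width = t(0.975, n1 + n2 − 2) × √(1/n1 + 1/n2).

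- One dose against placebo, no loss: 25 vs 25, 2.011 × 0.2828 = 0.57.
- 10% loss: 22.5 vs 22.5, 2.017 × 0.2981 = 0.60.
- 20% loss: 20 vs 20, 2.024 × 0.3162 = 0.64.
- Pooled doses against placebo, no loss: 50 vs 25, 1.993 × 0.2449 = 0.49.
- Pooled, 20% loss: 40 vs 20, 2.002 × 0.2739 = 0.55.

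**Dose drop, before any loss.** If m subjects have been randomized 1:1:1 at the switch and the other 75 − m go 2:1, then kept dose = m/3 + 2(75 − m)/3, dropped dose = m/3, and placebo = m/3 + (75 − m)/3 = 25.

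| Randomized at switch | Kept | Dropped | Placebo |
|---|---|---|---|
| 30 | 40 | 10 | 25 |
| 36 | 38 | 12 | 25 |
| 45 | 35 | 15 | 25 |
| 60 | 30 | 20 | 25 |

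Placebo stays at 25 and pooled active at 50 for every m. At least 30 must have completed Week 2 before the switch, so m cannot be below 30 and the dropped arm cannot fall below about 10.

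**The case against.** The other side has several good points.

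- **Evaluable is undefined.** Equating it with mITT is an inference. Even under that reading, one post-baseline visit is enough, possibly Week 2, and P300 recordings are uploaded for a quality check before randomization. Loss could therefore be small; at 5%, about 71 would remain. The word approximately also leaves a little room. This limits the size of the gap. It does not remove it, because mITT is a subset of those randomized and no allowance is stated.
- **No power or precision is lost on paper.** A reader might infer that the mismatch undermines a stated power or precision. The documents claim neither; the size was chosen empirically. The half-widths above are illustrations, not departures from a promise.
- **The dose drop.** A reader might infer that the plan would have ended near 40/10/25. The documents do not support that as the expected split. The rule is optional, its trigger is a minimum counted on Week 2 completers, and no pause in enrolment is stated, so 40/10/25 is the extreme case. Only the dropped arm shrinks. The kept dose gains precision (40 vs 25: 1.998 × 0.2550 = 0.51 SD, against 0.57), and the pooled comparison is unchanged. The interim was cancelled. Protocol 8.7 (Interim Analysis) is in the contents list but not in the supplied text, so it may address arm sizes, and its absence is not held against the plan.
- **The SAP discloses the early stop.** A reader might infer that the SAP presents 25 evaluable per arm as achieved. SAP 6, 8, 9.5 and 10.5.1.1 say that the study was stopped early, that no statistical conclusion can be drawn, and that enrolment was limited; SAP 10.1 already plans a disposition table with randomized and mITT counts. What remains is narrower: 6.1.2 itself does not mark 75 as planned.

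**Conclusion.** The mismatch stands. Three places state 75 evaluable, two randomize approximately 75, and nothing in the supplied text bridges them. If evaluable means mITT, and under an assumed 5% to 20% loss, the design would deliver about 71 to 60 evaluable subjects, or about 24 to 20 per arm. The effect on precision is modest: for one dose against placebo the half-width widens by at most 0.07 SD (0.64 − 0.57), and for the SAP's pooled comparison by 0.06 SD (0.55 − 0.49) at 20% loss.

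As a secondary point, 25 per arm holds only if no dose is dropped. That is an unstated condition in the sample-size sections supplied, not something that happened.

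The loss range is an assumption throughout, since the documents give none. With the trial stopped early, correcting SAP 6.1.2 matters more in practice than correcting the protocol.

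**What to change.** **Protocol 8.6 and synopsis.** State the size as approximately 75 randomized. Define evaluable, for example as mITT. Give the expected evaluable number under a stated assumed loss (for example, about 60 to 71, or 20 to 24 per arm, at 5% to 20%). Say that 25 randomized per arm applies only if no dose is dropped.

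**SAP 6.1.2.** Label 75 as the planned size. Beside it, give the numbers actually randomized and in mITT per arm at closure, with the 95% CI half-width that those numbers support for the pooled comparison and for each dose against placebo.

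**Cost.** Wording only: no added patients and no change to the analysis. The downside is that the stated size becomes less favourable.
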